## 2 Study Objective

---

This is a feasibility study to evaluate the clinical performance of a new silicone hydrogel formulation lens (Orion) in comparison with Gemini A ██████ over a period of two weeks of wear.

The primary variables of interest are:

- Vision

The secondary variables of interest are:

- Comfort/comfort preference
- Surface wettability performance
- Lens fit
- Lens handling
- Anterior ocular health

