### 2.1 Study Hypothesis

---

The primary hypothesis is that there will be no difference in vision performance between the Orion Test lens and the Gemini Control lens.

The secondary hypothesis is that there will be no difference in performance between the Orion Test lens and the Gemini Control lens for any of the secondary variables.

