### **3.1 Study Design & Comparator Justification**

---

The study design was chosen since the influence of confounding covariates is reduced in crossover designs, as each subject acts as his or her own control. Crossover study designs are also statistically more efficient.

The choice of comparator was made since the aim of the project is to match the clinical performance of the Gemini (Acquiane) lens, which is CE-marked / already approved in Europe.

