**Table 4: Secondary variable (comfort) sample size calculation**

Non-inferiority margin for comfort	Mean individual standard deviation	Sample size, Power 80% (p = 0.05)
-0.75	1.3	53

Consequently, a sample size of approximately 60 completing subjects is sufficient for this study.

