## 10.2 Statistical analysis

---

Summary statistics will be produced (e.g. mean, standard deviation). Paired t-test will be used to compare slit lamp biomicroscopy, lens fit and subjective scores between study lens types. Repeated Measures Analysis of Variance (ANOVA) or paired analysis will be used to compare the variables between study visits. The critical alpha level for statistical significance will be set at  $p \leq 0.05$ , with adjustment for multiple comparisons.

All participants who were evaluated will be used in the analysis. In the event of missing data, individual data points will be excluded in the analysis and not extrapolated from the collected data.

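### Section 10.2 does not exempt the slit lamp comparisons from its multiplicity adjustment; on the natural reading this makes worse anterior ocular health on the Test lens harder to flag

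*Combined protocol and SAP*

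**What the plan says.** Section 2 lists "Anterior ocular health" among the secondary variables. Section 2.1 states the secondary hypothesis that "there will be no difference in performance between the Orion Test lens and the Gemini Control lens for any of the secondary variables". Section 3.1 explains the comparator by saying that "the aim of the project is to match the clinical performance of the Gemini" lens.

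Section 10.2 gives the method: "Paired t-test will be used to compare slit lamp biomicroscopy, lens fit and subjective scores between study lens types". The next sentence provides for repeated measures ANOVA or a paired analysis between visits. The sentence after that begins "The critical alpha level for statistical significance will be set at", gives p ≤ 0.05, and ends "with adjustment for multiple comparisons".

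The plan does not name the adjustment method, the set of comparisons that forms the family, or their number. It neither names slit lamp findings as part of the adjustment nor excludes them. Section 10.1 gives margins for visual acuity and comfort only.

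**The concern.** Multiplicity adjustment protects against declaring a difference that is not there. That suits a claim that one lens is better. For a safety variable, in a study that hopes to find the lenses alike, the costly error is the other one: missing a real worsening on Test. Any adjustment over more than one comparison lowers the alpha for each test and makes that error more likely.

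Acuity and comfort have margins. If they are tested against those margins, a stricter alpha makes the wanted conclusion harder to reach. Ocular health has no margin, so the only rule that Section 10.2 offers for it is a test of difference. There, a stricter alpha makes the wanted result, no significant difference, more likely. What is at stake is the ability of an early study of a new lens formulation to pick up a modest average shift in slit lamp grades.

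**Working it through.** **Inputs from the documents**
- Significance level 0.05 before adjustment, and a paired t-test for slit lamp findings (10.2).
- Completers: Section 10.1 concludes that "a sample size of approximately 60 completing subjects is sufficient for this study".

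**Assumptions, because the documents do not give these**
- Two-sided tests.
- One slit lamp value per subject and lens, so 60 pairs and 59 degrees of freedom.
- Bonferroni, alpha = 0.05/k, with k = 5, 10 or 20.
- Differences in units of the SD of the paired differences, since no slit lamp SD is given.

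**The plan's own figure.** The plan has no power figure for slit lamp findings. Its 60 completers follow from the 53 for comfort (Table 4: margin 0.75, SD 1.3, power 80%). That 53 reproduces as an equivalence calculation with two one-sided tests at 0.05, true difference 0 and SD of the difference 1.3 × √2. The standard error is 1.3 × √(2/53) = 0.2525, and the noncentrality is 0.75/0.2525 = 2.97. Each one-sided test has power 0.9008, so both succeed with probability 2 × 0.9008 − 1 = 0.80. The 60 was therefore sized on comfort at an alpha with no multiplicity adjustment.

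**Power of the slit lamp test.** For a true standardised difference d, the noncentrality is d × √60. Power is the probability that a noncentral t with 59 df lies beyond ± the critical value at 0.05/k.
- d = 0.368, the difference with 80% power at 0.05: 0.368 × 7.746 = 2.85
- d = 0.5: 0.5 × 7.746 = 3.87

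| k | alpha | critical t | power, d = 0.368 | power, d = 0.5 | d with 80% power |
|---|---|---|---|---|---|
| 1 | 0.05 | 2.001 | 80.1% | 96.8% | 0.368 |
| 5 | 0.01 | 2.662 | 57.7% | 88.2% | 0.455 |
| 10 | 0.005 | 2.916 | 47.9% | 82.5% | 0.488 |
| 20 | 0.0025 | 3.159 | 38.9% | 75.8% | 0.520 |

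At d = 0.368 the chance of a non-significant result, despite a real difference, rises from 20% to 42%, 52% and 61%. With k = 3 the power is 65%.

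**Contrast with a margin test.** For comfort with 60 completers, the noncentrality is 0.75/(1.3 × √(2/60)) = 0.75/0.2373 = 3.16. Non-inferiority power at one-sided 0.05/k falls from 93% (k = 1) to 78%, 69% and 60% (k = 5, 10, 20). There the adjustment works against the wanted conclusion. For slit lamp findings it works in its favour.

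**The case against.** **Scope.** The adjustment phrase follows directly after the between-visit ANOVA sentence, a usual place for such a correction, and may have been meant only for those comparisons. This stands as an ambiguity. The alpha sentence is general and nothing in it limits it to visits, so coverage of the slit lamp tests is the natural reading, not an established fact. A reader might also infer one family pooled over slit lamp, fit and questionnaire items. No section says so; correction within one variable or one domain is equally possible.

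**Size.** The 0.37 SD difference is simply the one with 80% power at 60 completers; nothing in the plan marks it as clinically relevant. At 0.5 SD power stays at about 76% or more in every case shown. A method less conservative than Bonferroni would lose less. This stands, so the figures illustrate the loss and do not estimate it.

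**Other protection.** A reader might infer that ocular safety depends on this p-value. It does not. Section 8.1 classifies events by clinical thresholds and sets reporting times, Section 8.3 has the sponsor review adverse events, slit lamp examination is repeated at Visits 2 and 3, and 10.2 promises summary statistics whatever the p-values. This protection is real but partial. Code 14 requires corneal staining of about grade 3, and codes 15 and 22 require a two-grade change from baseline. A smaller average shift between lenses might trigger none of these and show only in the slit lamp comparison.

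**Setting.** This is a feasibility study with two weeks per lens, described as non-significant risk. That limits the urgency. It does not argue for stricter evidence before a signal is noticed.

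**Conclusion.** The point holds on the natural reading of 10.2. The slit lamp paired t-tests are not exempted from the adjustment, and any adjustment over more than one comparison reduces the chance of flagging a true worsening on Test. The direction is certain for k > 1. The size is not: under the assumptions above, power drops from 80% to 39–58% at 0.37 SD and from 97% to 76–88% at 0.5 SD, for 5 to 20 comparisons.

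Two stronger readings are not supported. First, the plan nowhere states that a non-significant slit lamp result means the lenses will be declared alike; the hypothesis and the missing margin only leave that reading open. Second, removing the adjustment would not make non-significance evidence of similarity. Even unadjusted, a 0.37 SD worsening is missed 20% of the time and a 0.2 SD worsening about 67% (power 33%).

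This is a cheap and worthwhile improvement, not a defect that invalidates the study.

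**What to change.** In Section 10.2:
- State that the slit lamp comparisons between lenses are not adjusted for multiplicity.
- Report the Test-minus-Control estimate with an unadjusted 95% CI for each slit lamp item. With 60 completers the half-width is 2.001/√60 = 0.26 SD of the paired differences, so readers can see what size of worsening is not excluded.
- Treat unadjusted p ≤ 0.05 on a slit lamp item as a signal for review.
- State that a non-significant slit lamp result will not be read as evidence of no difference.

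For the comparisons that remain adjusted, name the method and the family. Adverse events need no exemption, because 10.2 plans no test of them.

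The change is a few sentences and affects no visit, procedure or sample size. The downside is about one false signal per 20 null comparisons. If the items were independent, the chance of at least one would be 1 − 0.95^k: 23% for 5 items, 40% for 10 and 64% for 20. Each such signal leads only to a review.

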## 11 Data Quality Assurance

---

### 11.1 Study monitoring

---

Site qualification of the investigative site has been completed to ensure that the site facility is adequate, personnel are qualified, and resources are satisfactory to conduct clinical studies for the Sponsor. The protocol will be reviewed by the investigators prior to enrollment of the first subject. This will involve an overview of the protocol, which includes information on study objectives, inclusion and exclusion criteria, study visits and adverse event reporting. Data collection forms will also be reviewed, and this will provide an opportunity to discuss any questions.

During the course of the study, remote monitoring will be conducted to verify that written informed consent was obtained using the IRB approved ICF prior to each subject's participation in the study.

Prior to final data freeze, a remote close-out visit/discussion may be warranted to check for accuracy and completeness of records. The sponsor or sponsor's representatives will be authorized to gain access to the source documentation for the purposes of monitoring and auditing the study.

## **11.2 Record keeping**

---

Detailed records of all study visits will be made using the Case Report Forms (CRFs). All data recorded on forms will be in ink. Any corrections to the forms will be initialed and dated at the time they are modified.

## **11.3 Record retention**

---

Following study completion, data will be available in electronic and/or paper format for audit, sponsor use, or subsequent analysis. The original clinical raw data (including completed CRFs and Informed Consent forms) will be retained according to guidelines set forth in the general work agreement with the site. The Sponsor will be notified and consulted if ever the files are to be destroyed. In the event that this Study Protocol is indicated for design verification and validation purposes, as indicated on the title page, all original raw data forms and completed CRF's will be forwarded to the sponsor at completion of the final report.

## **11.4 Data Entry / Data Management**

---

Data will be entered into an electronic spreadsheet. Study staff will only be able to modify the data file via password entry. The investigators will be responsible for the data integrity, and complete data entry for each visit as well as for any questionnaires. The investigator will send the data collected to the study sponsor within approximately 5 business days after the last subject completes the final visit.

## **11.5 Confidentiality**

---

This study is confidential in nature. Both Indiana University and Sponsor agree to hold in confidence, in accordance with the conditions laid out in the [REDACTED] Agreement [REDACTED] any information disclosed to the other party under that Agreement and identified verbally or in writing as confidential.

All records will also be handled in accordance with HIPAA (1996) standards.

## 11.6 Publication

---

Indiana University may publish the results of this study, subject to the conditions laid out in the [REDACTED] Agreement, [REDACTED]

## 12 Study Costs

---

The sponsor will compensate the clinical site and the subjects for their time and participation in this voluntary study.

Expenses incurred for medical treatment as part of study participation will be paid by the sponsor (bills and prescription receipts kept). The participant must be followed until resolution and a written report completed indicating the subsequent treatment and resolution of the condition.

**APPENDIX 1**

**Slit Lamp Biomicroscopy Grading Scales**

[figure not shown]
(b) (5) - DPP

[figure not shown]
**APPENDIX 2**  
**Randomization**

[figure not shown]

[figure not shown]
**APPENDIX 3**

**Post-Settling Subjective Questionnaire**

[figure not shown]

[figure not shown]

**APPENDIX 4**

**Objective Assessments: Lens Surface and Lens Fit Grading Scales**

[figure not shown]

[figure not shown]
[figure not shown]
## Lens Fit Grading

[figure not shown]
[figure not shown]
**APPENDIX 5**

[figure not shown]
[figure not shown]
**(Two Week) Final Subjective Questionnaire**

[figure not shown]

CooperVision Bilateral Subjective Questionnaire

CooperVision Bilateral Subjective Questionnaire

[figure not shown]

**APPENDIX 6**

[figure not shown]
**Lens Preference Subjective Questionnaire**

[figure not shown]
CooperVision Bilateral Subjective Questionnaire - *Preference*

[figure not shown]
[figure not shown]
**APPENDIX 7**

**Web-based Comfort throughout the Day Questionnaire**

**APPENDIX 8**  
**Adverse Event Forms**

CVI ADVERSE EVENT OUTCOME FORM
